3.1.3 Definition of Baseline

Baseline is defined as the last non-missing measurement prior to the first dose of study treatment. This can be on Day 1 as long as the measurement is taken prior to the first dose. If a subject's day 1 samples are taken after the initial infusion, the samples taken prior to cycle 1 day 1, such as screening samples, may be used as the baseline values.

3.1.4 Summary Statistics

Summary statistics will be presented by treatment group and stratum. Unless otherwise stated, continuous variables will be summarized using the number of non-missing observations,

arithmetic mean, standard deviation, median, minimum, and maximum values as descriptive statistics. Categorical variables will be summarized using the frequency count and the percentage of patients in each category as descriptive statistics.

3.1.5 Handling of Dropouts and Missing Data

In general, data will be analyzed and presented as observed and will not be imputed for the analysis of efficacy and safety, unless otherwise specified.

In case the start and end dates for adverse events and concomitant medications/procedures are missing or incomplete, the missing component(s) will be assumed as the most conservative value possible. For example, AEs with missing start dates, but with stop dates either overlapping into the treatment period or missing, will be counted as treatment-emergent, taking the worst-case approach. When partial dates are present in the data, both a partial start date and/or a partial stop date will be evaluated to determine whether it can be conclusively established that the AE started prior to the start of study treatment or ended prior to the start of study treatment. If the above cannot be conclusively established based on the partial and/or present dates, then the AE will be considered as treatment-emergent. Actual data values as they appear in the original case report forms (CRFs) will be presented in the data listings.

Viral load values below the limit of quantification will be imputed as the limit of quantification minus 0.1 unit (for CMV) or minus 1 unit (for other viruses).

3.2 Analysis Populations

3.2.1 Intent-to-Treat (ITT) Population

The Intent-to-Treat (ITT) Population will include all randomized patients regardless of whether the patient actually receives PSL or placebo. Patients will be analyzed according to the randomized study treatment.

3.2.2 Modified Intent-to-Treat (mITT) Population

The modified Intent-to-Treat (mITT) Population will include all randomized patients who have the disease under study and who receive any amount of PSL or placebo. Patients will be analyzed according to the randomized study treatment. Analyses using mITT may be set aside if it is determined that the ITT population and the mITT Population are identical.

3.2.3 Safety Population

The Safety Population will include all patients who receive any amount of PSL or placebo. All safety analyses will be based on the Safety Population. Patients will be analyzed according to the treatment actually received.

3.3 Patient Data and Study Conduct

Unless otherwise noted, safety listings and tables will be presented for Safety Population based on the actual treatment. Efficacy listings will be presented for ITT Population based on the randomized study treatment. Efficacy summary tables and statistical analysis will be presented for ITT population as indicated in [Table 1](#).

3.3.1 Patient Disposition

All patients who provided informed consent will be included in a summary of patient disposition. The numbers and percentages of patients who were screened, screen failure along with the reasons of screen failure, randomized, completed study drug, discontinued study drug early, completed the study and discontinued the study early will be summarized along with the reasons for early discontinuation of study and study drug.

The numbers and percentages of patients in each analysis population with reasons for exclusion will also be summarized.

By patient listing will also be provided for patient disposition, screen failures, patients who were randomized and reason for exclusion from analysis population.

3.3.2 Protocol Deviations

The numbers and percentages of patients with protocol deviations by deviation category will be summarized for ITT population.

All protocol deviations will be listed by patient.

3.3.3 Demographic and Baseline Characteristics

Demographic (age, sex, race, and ethnicity) and baseline characteristics (height, weight and body mass index at baseline) will be summarized with descriptive statistics or counts and percentages of patients as appropriate. The summaries will be provided for ITT and safety populations, unless these are identical (all randomized patients are treated), in which case only the ITT version will be provided.

In addition, these following categories will be presented in listings:

- Childbearing potential
- Number of matched HLA alleles and class (I, II and I&II) between the cell line and study patient, and between the cell line and kidney transplant donor
- Any other relevant disease characteristics, such as GFR, BK viral load, and immunosuppressive medications at Baseline

All the HLA analyses will be based on CytoMatch data, not the EDC HLA data.

3.3.4 Medical History

Medical history will be coded to system organ class and preferred term using the Medical Dictionary for Regulatory Activities (MedDRA). The numbers and percentages of patients with medical history by system organ class and preferred term will be summarized.

A by-patient listing of medical history will be provided.

In addition, underlying disease for kidney transplantation will be listed.

3.3.5 Concomitant Medications

Concomitant medications will be coded to anatomical therapeutic chemical (ATC) class and preferred term using the WHO Drug Dictionary. All medications taken prior to the first dose of

study treatment will be considered as prior medications. The medications taken prior to the first dose of study treatment and were ongoing or started on or after the first dose of study treatment will be considered as concomitant medications.

The numbers and percentages of patients taking prior and concomitant medications by ATC class and preferred term will be summarized based on the safety population.

A by-patient listing will be provided for prior and concomitant medications.

3.3.6 Immunosuppression Therapy

Immunosuppression therapy will be presented similarly as concomitant medication.

An immunotherapy dose reduction will be defined as a reduction of 50% or greater of the current dose when compared to the dose at Baseline.

3.3.7 Study Drug Exposure and Compliance

Study drug duration, number of doses, and total dosing will be summarized based on the Safety Population.

The length of exposure to study drug (PSL or Placebo) will be calculated as the number of days from the first dose of double-blind study to 14 days after the last dose of double-blind study drug, regardless if the patient missed one or more doses of study drug. Length of exposure will be summarized by treatment group using descriptive statistics for the safety population.

A by-patient listing will be provided for study drug exposure.

Overall compliance will be calculated as:

$$(Sum\ of\ total\ volume\ administered) / (total\ volume\ of\ planned) * 100$$

The number and percentage of patients will be summarized by treatment group for the Safety Population for the following categories 0- <75%; >= 75%.

For patients who discontinue treatment per protocol for resolution of viremia, the total planned volumes will be calculated up to the last dosing date.

The study drug administration and compliance data, including reasons for poor compliance if noted in the CRF, will be listed for each patient.

3.4 Efficacy Analyses

This section describes the analysis to be conducted for the key secondary, other secondary and exploratory efficacy endpoint along with other endpoints. The efficacy analysis will be performed on the ITT population unless otherwise stated. Analyses using mITT may be set aside if it is determined that the ITT population and the mITT Population are identical. Unless otherwise specified, the results of efficacy analysis and all the summary tables will be presented by stratum and treatment group.

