9.2 Sample Size Determination

Note: “Enrolled” patients are those who have been randomized to a treatment arm.

No formal sample size determination was made for this study, whose primary endpoint is safety and tolerability. Approximately 60 patients will be randomized at approximately 38 clinical sites. Patients (n=20 in each arm) will be randomized to receive PSL [REDACTED] or placebo. [REDACTED]

Sample size estimates are based on a one-sided test at the 0.05 level to detect suppression of viral load to undetectable levels based on the viral load data from the CHARMS study of multivirus-specific T cells for patients with a plasma BK viral load <2000 copies/mL.

Patients will be stratified by screening BK viral load at randomization to ensure equal randomization among active and placebo arms for patient populations [REDACTED]
[REDACTED]

[REDACTED] A minimum of 6 patients must be enrolled in each stratum, but the remaining patients can be enrolled in either stratum.

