9.4.1 General Considerations

Summary statistics will be presented by treatment group. Unless otherwise stated, continuous variables will be summarized using the number of non-missing observations, arithmetic mean, standard deviation, median, minimum, and maximum values as descriptive statistics. Categorical variables will be summarized using the frequency count and the percentage of patients in each category as descriptive statistics.

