2.1.2 Secondary Objectives

The key secondary objective is to assess the overall efficacy of PSL to suppress BK viral load compared with placebo.

The other secondary objective is to compare the relative efficacy of different dosing regimens of PSL to suppress BK viral load versus placebo.

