3.4.1 Secondary Efficacy Endpoints

The key secondary efficacy endpoint is change from Baseline in BK viremia in both copies/mL and log10 copies/mL in patients receiving PSL (pooled PSL) compared to patients receiving

placebo, based on quantitation of viremia performed at the central laboratory. The other secondary efficacy endpoint is change in BK viremia in patients receiving different dosing regimens of PSL compared to patients receiving placebo in copies/mL and log10 copies/mL. Change in BK viremia will be assessed by BK viral load assessments.

Observed, change from baseline and percent change from baseline values for BK viral load will be summarized by visit and treatment using descriptive statistics. Percentage change of BK viral load from baseline at each post baseline visit will be presented to determine the rate of decline of BK viremia. Listing will be provided for BK viral load.

AUC for BK viral load (in log 10 copies/ml) adjusted by time duration (area divided by days) will be summarized at each post-baseline timepoint by treatment arm using descriptive statistics. Listings will be provided for AUC of BK viral load.

Two different plots of BK viral load and change from Baseline (both copies/mL and log scale) will be presented for both mean+/- SD and median & IQR by visit for (Arm 1, Arm 2 and Arm 3) and (Arm 1+2 and Arm 3).

Two sets of figures will be produced for mean+/- SD for percent change from baseline (day 1) for BK-viral load for (Arm 1, Arm 2 and Arm 3) and (Arm 1+2 and Arm 3).

Two sets of figures will be produced for both mean+/- SD and median & IQR for AUC for (Arm 1, Arm 2 and Arm 3) and (Arm 1+2 and Arm 3).

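### SAP 3.4 makes by-stratum efficacy results the default, and SAP 3.4.1 does not say whether pooled PSL versus placebo is also estimated across both strata

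*SAP*

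**What the plan says.** SAP 2.1.2 sets the aim: "The key secondary objective is to assess the overall efficacy of PSL to suppress BK viral load compared with placebo". SAP 3.4.1 defines the contrast by pooling the two dosing arms: "in patients receiving PSL (pooled PSL) compared to patients receiving" placebo. It does not mention strata.

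The default layout is by stratum. SAP 3.4 states that, unless otherwise specified, "the results of efficacy analysis and all the summary tables will be presented by stratum and treatment group". SAP 3.1.4 repeats it: "Summary statistics will be presented by treatment group and stratum". Protocol 9.4.1 has treatment group alone: "Summary statistics will be presented by treatment group".

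Within SAP 3.4.1, observed values, change and percent change in BK viral load "will be summarized by visit and treatment using descriptive statistics". The time-adjusted AUC is tabulated by arm, and the figures show three arms or Arms 1+2 against Arm 3. Stratum is not mentioned. SAP 3.4.1 contains no model, test or confidence interval for the contrast.

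Protocol 9.4.5, under the safety heading, compares BK viral load between the placebo and treatment groups with Fisher's exact or Student's t test, without stratum. Protocol 9.1 plans no formal hypothesis testing.

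On stratum size, Protocol 9.2 says: "A minimum of 6 patients must be enrolled in each stratum, but the remaining patients can be enrolled in either stratum".

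**The concern.** The trial randomizes within viral-load strata, but neither document names an estimate that combines the strata and takes account of them. The programmer is left with two readings. In the first, the SAP 3.4 default governs and BK viral load is shown separately for Stratum 1 and Stratum 2. In the second, the by-visit-and-treatment wording of SAP 3.4.1 counts as otherwise specified, and the data are pooled without regard to stratum. The SAP does not say which applies, or which result answers the key secondary objective.

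Under the first reading, precision is lost and two results may seem to differ by chance alone. Under the second, differences between strata are left in the residual variation.

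The stratification variable is likely to matter here. Screening load may run from 350 to 10,000,000 copies/mL (Protocol 5.1), and BK values below the limit are set to 156 − 1 = 155 (SAP 3.1.5 and 3.4.2). If baseline equals the screening value, the largest recordable fall is log10(350/155) = 0.35 at the bottom of the range and log10(10,000,000/155) = 4.81 at the top. The change a patient can show therefore depends on starting load.

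**Working it through.** **Inputs from the documents.** About 60 patients, 20 per arm (Protocol 9.2): 3 × 20 = 60, which agrees. Pooled PSL versus placebo is therefore 40 v 20. The minimum stratum is 6. The documents give no effect size, SD or expected split for BK viral load, so nothing further in the sample size can be reproduced.

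**Assumptions.** Allocation is 2:1 (pooled PSL to placebo) within each stratum, the SD is common, the true effect is the same in both strata, and no data are missing.

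**Step 1: precision.** SE = SD × √(1/n_PSL + 1/n_PBO). The half-width is the t quantile × SE.

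| Set | PSL v placebo | SE (SD) | 95% CI half-width (SD) |
|---|---|---|---|
| All patients | 40 v 20 | √(1/40 + 1/20) = 0.274 | 0.55 |
| One stratum, 30/30 split | 20 v 10 | √(1/20 + 1/10) = 0.387 | 0.79 |
| Minimum stratum of 6 | 4 v 2 | √(1/4 + 1/2) = 0.866 | 2.40 |
| Other stratum of 54 | 36 v 18 | √(1/36 + 1/18) = 0.289 | 0.58 |

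**Step 2: the combined estimate keeps the full precision.** Combining the within-stratum differences on a common SD gives SE = 1/√(1/SE₁² + 1/SE₂²). For 6/54 this is 1/√(1.333 + 12) = 0.274. For 30/30 it is 1/√(6.667 + 6.667) = 0.274. Splits of 12/48 and 18/42 give the same value.

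**Step 3: chance of opposite directions.** With true effect d, stratum i shows the wrong sign with probability q_i = Φ(−d/SE_i). The two strata point in opposite directions with probability q₁(1 − q₂) + q₂(1 − q₁).

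- d = 0.5 SD, 30/30: q = Φ(−1.29) = 0.098 in each; 2 × 0.098 × 0.902 = 0.18.
- d = 0.5 SD, 6/54: q₁ = Φ(−0.58) = 0.282 and q₂ = Φ(−1.73) = 0.042; 0.282 × 0.958 + 0.042 × 0.718 = 0.30.
- Range over d: 34% (30/30) to 41% (6/54) at 0.3 SD, and 4% to 18% at 0.8 SD.

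**Step 4: cost of a crude pool.** If mean log10 change differs by D between strata, the within-stratum SD is 1.0 and a share p of patients is in one stratum, the pooled SD is √(1 + p(1 − p)D²).

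| D (log10) | Split | Pooled SD | SE overstated by | Equivalent loss of patients |
|---|---|---|---|---|
| 0.5 | 30/30 | √(1 + 0.25 × 0.25) = 1.031 | 3% | 1 − 1/1.0625 = 6% |
| 1.0 | 30/30 | √(1 + 0.25) = 1.118 | 12% | 1 − 1/1.25 = 20% |
| 1.0 | 6/54 | √(1 + 0.09) = 1.044 | 4% | 1 − 1/1.09 = 8% |

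**The case against.** The by-stratum rule gives way where the SAP specifies otherwise. SAP 3.4.1 describes its tables and figures by treatment or arm, and nothing excludes an all-patients column. Protocol 9.4.5 does compare the treatment groups over all patients. In SAP 2.1.2, overall efficacy may simply mean pooled over dosing regimens, because the next objective compares regimens. The study is descriptive with safety as its primary endpoint, so a model with a confidence interval goes beyond what was planned.

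Much of this stands. A reader might infer that two stratum results replace the overall answer; the documents do not say so. Nor need both strata be small, since one may hold 54 of the 60 patients. A reader might also infer an inflated false-positive rate from a choice among the overall and two stratum results, or count how often one stratum is significant and the other is not. Neither has a basis here: Protocol 9.1 plans no formal testing, and neither document describes a test within a stratum. Crude pooling is not biased, because randomization was stratified. The error bars in the SAP figures show SD or IQR, so they say nothing about the precision of a treatment difference.

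The ambiguity is not removed, however. SAP 3.4.2 summarizes eGFR by visit without even naming treatment, although that endpoint compares PSL with placebo. Such sentences do not specify the grouping in full, so silence on stratum in SAP 3.4.1 cannot safely be taken as an override. And even if overall means pooled over regimens, the pooled contrast must still be formed within strata or across them.

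**Conclusion.** The point holds as an unstated choice, not as a missing overall result. The SAP defaults to by-stratum presentation and does not say whether pooled PSL versus placebo is estimated across strata. The one all-patients comparison, in Protocol 9.4.5, is unstratified and is not taken into the SAP.

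Compared with the all-patients contrast, a stratum result has a standard error 1.4 times as large at 30/30 (0.387/0.274) and 3.2 times as large in a minimum stratum of 6 (0.866/0.274). The other stratum of 54 then loses little (0.289 against 0.274 SD). Apparent contradiction between strata with the same true effect would be common at modest effects: 18% to 30% at 0.5 SD. The penalty for a crude pool is smaller, 3% to 12% on the standard error in the cases tried.

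All these sizes depend on the assumed common SD, equal effect, 2:1 allocation within strata and split. The stratum cut-offs are blacked out in the public text, so the likely split cannot be judged.

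**What to change.** In SAP 3.4.1:

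- State that the key secondary result is pooled PSL versus placebo across both strata in the ITT population.
- Estimate it as one difference in log10 BK viral load change from baseline, with stratum as a term in the model, and report its confidence interval at a single visit named before unblinding.
- Do the same for each dosing regimen versus placebo.
- Add all-patients columns to the efficacy tables, and label the by-stratum tables supportive.
- Say in SAP 3.1.4 and 3.4 that by-stratum presentation is additional to the all-patients result.

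A model term shares one residual variance across strata. That is safer than weighting two separately estimated stratum differences, which would be unstable with only 2 placebo patients in a stratum.

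The cost is SAP wording, one set of columns and a simple model for each contrast, with no new data or patients. Stratum results become supportive. If an all-patients result was always intended, the change puts that on record and adds the adjustment.

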3.4.1 Secondary Efficacy Endpoints

The key secondary efficacy endpoint is change from Baseline in BK viremia in both copies/mL and log10 copies/mL in patients receiving PSL (pooled PSL) compared to patients receiving

placebo, based on quantitation of viremia performed at the central laboratory. The other secondary efficacy endpoint is change in BK viremia in patients receiving different dosing regimens of PSL compared to patients receiving placebo in copies/mL and log10 copies/mL. Change in BK viremia will be assessed by BK viral load assessments.

Observed, change from baseline and percent change from baseline values for BK viral load will be summarized by visit and treatment using descriptive statistics. Percentage change of BK viral load from baseline at each post baseline visit will be presented to determine the rate of decline of BK viremia. Listing will be provided for BK viral load.

AUC for BK viral load (in log 10 copies/ml) adjusted by time duration (area divided by days) will be summarized at each post-baseline timepoint by treatment arm using descriptive statistics. Listings will be provided for AUC of BK viral load.

Two different plots of BK viral load and change from Baseline (both copies/mL and log scale) will be presented for both mean+/- SD and median & IQR by visit for (Arm 1, Arm 2 and Arm 3) and (Arm 1+2 and Arm 3).

Two sets of figures will be produced for mean+/- SD for percent change from baseline (day 1) for BK-viral load for (Arm 1, Arm 2 and Arm 3) and (Arm 1+2 and Arm 3).

Two sets of figures will be produced for both mean+/- SD and median & IQR for AUC for (Arm 1, Arm 2 and Arm 3) and (Arm 1+2 and Arm 3).

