1 PROTOCOL SUMMARY

1.1 Synopsis

Protocol Title: Phase 2 multicenter, randomized, double-blind, placebo-controlled, multiple dosing interval, 2-period study of the safety, tolerability and effectiveness of adoptively transferred posoleucel (ALVR105) multivirus-specific T cells in kidney transplant recipients with either high or low levels of BK viremia

Protocol Number: P-105-201

Rationale:

This is a proof-of-concept study of posoleucel (PSL, ALVR105, formerly Viralym-M), and the principal objective is to assess the safety and tolerability of PSL in kidney transplant recipients. The key secondary objective is to test the hypothesis that the administration of PSL to kidney transplant recipients with BK viremia will demonstrate superiority in suppressing BK viral load compared with placebo.

Objectives and Endpoints:

Objectives	Endpoints
Primary 
To compare the safety and tolerability of PSL to placebo in kidney transplant recipients	
Treatment-emergent adverse events (TEAEs) and changes in vital signs, physical exams, clinical laboratory assessments, and electrocardiograms (ECGs).
Key Secondary 
To assess the overall efficacy of PSL to suppress BK viral load compared with placebo	
Change in BK viremia in patients receiving PSL compared to patients receiving placebo.
Other Secondary 
To compare the relative efficacy of different dosing regimens of PSL to placebo	
Change in BK viremia in patients receiving different dosing regimens of PSL compared to patients receiving placebo

Overall Design:

This is a Phase 2, multicenter, randomized, double-blind, placebo-controlled, parallel-group multiple dosing interval, 2-period study of the safety, tolerability and efficacy of adoptively transferred PSL virus-specific T cells in kidney transplant recipients with BK viremia.

An independent Data and Safety Monitoring Board (DSMB) will be convened for this study to routinely monitor patient safety; the DSMB will conduct the Interim Analyses according to the DSMB Charter.

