2.1 Study Rationale

This is a proof-of-concept study of PSL, and the principal objective is to assess the safety and tolerability of PSL in kidney transplant recipients with BK virus-associated nephropathy. The key secondary objective is to test the hypothesis that the administration of PSL to kidney transplant recipients will demonstrate superiority in suppressing BK viral load compared with placebo.

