9 STATISTICAL CONSIDERATIONS

9.1 Statistical Hypotheses

No formal hypothesis testing is planned for this study.

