9.4.5 Safety Analysis

All safety data will be summarized by treatment arm actually received. Categorical endpoints will be summarized using number and percentage of patients within each category. Continuous endpoints will be summarized descriptively with summary statistics (number, mean, standard deviation, standard error, median, first quartile, third quartile, minimum, and maximum).

Adverse events will be coded using the Medical Dictionary for Regulatory Activities. A TEAE is defined as an AE with a start date and time on or after the first dose of study treatment and through the Week 24 visit. Treatment-emergent AEs will be summarized by System Organ Class and Preferred Term and further by severity (according to the National Cancer Institute [NCI] Common Terminology Criteria for Adverse Events [CTCAE] v5.0) and relationship to study treatment. The incidence of SAEs will be summarized.

The incidence of AESIs including acute GVHD, CRS, infusion reactions and their corresponding exact binomial confidence intervals with 95% confidence level will be presented by treatment group. Grading criteria for GVHD and CRS are in Appendix 5 in [Section 10.5](#) and Appendix 6 in [Section 10.6](#), respectively.

Descriptive statistics will be provided for relevant laboratory, vital sign, and ECG data. Abnormal laboratory results will be graded according to NCI CTCAE v5.0, if applicable. A shift table, presenting the 2-way frequency tabulation for baseline and the worst post-baseline value according to the NCI CTCAE grade, will be provided for selected clinical laboratory tests.

Clinical safety laboratory parameters will be presented in summary tables. Changes from baseline in laboratory parameters, vital sign parameters, and quantitative ECG parameters will be summarized. Selected laboratory parameters will be summarized in shift tables.

Statistical comparisons will be carried out using Fisher's exact test and Student's t test. A 1-sided $P < .05$ will be considered statistically significant. Key secondary outcomes such as BK viral load assessments and change in eGFR (measured by comparing the slope of decline in the eGFR over time) between the placebo group and treatment group will be analyzed using the statistical comparisons described above. The baseline demographics of patients, such as age and gender, etc., will also be analyzed to ensure adequate randomization.

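### The protocol contradicts itself on whether the key secondary BK viral load effect is tested, and the SAP names no lead scale, visit or between-arm estimate with an interval

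*SAP*

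**What the plan says.** **Protocol, for testing.** The Synopsis (1.1) expects that PSL "will demonstrate superiority in suppressing BK viral load compared with placebo". Study Rationale (2.1) sets the key secondary objective as to "test the hypothesis that the administration of PSL to kidney transplant recipients will demonstrate superiority in suppressing BK viral load compared with placebo". Section 9.4.5, under Safety Analysis, says: "Statistical comparisons will be carried out using Fisher's exact test and Student's t test". It sets one-sided P < .05 as the threshold, then says that key secondary outcomes, naming BK viral load and change in eGFR, "between the placebo group and treatment group will be analyzed using the statistical comparisons described above".

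**Protocol, against testing.** Section 9.1: "No formal hypothesis testing is planned for this study". The objectives tables (1.1 and 3) speak of assessing efficacy, not of testing it.

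**Protocol, both ways.** Section 9.2 denies a formal sample-size determination, then refers to a one-sided 0.05 test of suppression to undetectable levels. Text near that sentence is redacted.

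**SAP.** Section 3.4.1 opens: "The key secondary efficacy endpoint is change from Baseline in BK viremia in both copies/mL and log10 copies/mL", with pooled PSL against placebo as the contrast. It continues: "The other secondary efficacy endpoint is change in BK viremia in patients receiving different dosing regimens of PSL compared to patients receiving placebo", again on both scales. The analysis is: "Observed, change from baseline and percent change from baseline values for BK viral load will be summarized by visit and treatment using descriptive statistics". The section also plans a time-averaged log10 AUC, summarised descriptively at each post-baseline timepoint. Sections 3.1.4 and 3.4 call for results by stratum. Section 2.2.3 keeps the denial of a formal sample-size determination and omits the one-sided test.

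**The concern.** Protocol 9.4 leaves the technical detail of the key secondary analysis to the SAP, so the SAP is where the conflict should be settled. It takes the descriptive side in practice but does not say that the test sentence in Protocol 9.4.5 no longer applies. Either reading could therefore be claimed after unblinding.

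Both readings leave a gap. If section 9.4.5 is applied as written, the result can depend on which scale and visit are used, and neither is ranked. If the SAP's description stands, a placebo-controlled proof-of-concept comparison has no stated effect size and no interval. The eGFR label is a smaller instance of the same problem: section 9.4.5 calls it key secondary, while Protocol 3 and SAP 2.3.3 list it as exploratory.

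**Working it through.** **1. The plan's own figure.** Protocol 9.2 gives 20 patients in each of three arms: 3 × 20 = 60, which agrees with the stated total. The one-sided 0.05 basis cannot be reproduced, because the legible text gives no response rates or power. At one-sided 0.05 and 80% power, without continuity correction, 20 per arm would fit 10% against 45% (20 vs 20) or 10% against 40% (40 vs 20). It would equally fit 20% against 58% or 53%. The number 20 therefore identifies no single design.

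**2. What SAP 3.4.1 settles and what it leaves open.**
- Contrast: settled. Pooled PSL against placebo is key; each regimen against placebo is other secondary.
- Scale: copies/mL and log10 copies/mL, unranked.
- Time: SAP Appendix B, Table 2 lists Weeks 2, 4, … 24, which is 12 post-baseline visits, none designated as lead. The log10 AUC combines visits but is not designated either.
- Stratum: displayed, not adjusted for. A stratum may hold as few as 6 patients (SAP 2.2.3).
- Statistics: SAP 3.1.4 defines n, mean, SD, median, minimum and maximum. These are per-arm figures, without a difference or CI. The only efficacy CI in the legible text is for Kaplan-Meier medians (SAP 3.4.2).

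SAP Table 1 (section 3.4.3) is damaged in the text available. This step rests on sections 3.1.4, 3.4 and 3.4.1.

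**3. Precision available without any test.** For pooled PSL against placebo, 40 vs 20, complete data:
- √(1/40 + 1/20) = 0.274; × t(0.975, 58) = 2.002 gives a 95% half-width of **0.548 SD**.
- With 10% missing (36 vs 18): √(1/36 + 1/18) = 0.289; × t(0.975, 52) = 2.007 gives **0.58 SD**.
- One regimen against placebo, 20 vs 20: 0.64 SD.

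Neither document states an SD. At assumed residual SDs of 0.6, 0.8 and 1.2 log10, the complete-data pooled half-width is 0.33, 0.44 and 0.66 log10, or 2.1-, 2.7- and 4.5-fold.

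**4. The assay floor.** SAP 3.1.5 sets BK values below the limit to the limit minus 1, and SAP 3.4.2 gives the limit as 156, so the floor is 155. From a value of 350 the largest possible fall is log10(350/155) = 0.354 log10, or 2.3-fold. The 350 minimum is a screening limit (Protocol 5.1). The analysis baseline is the last value before first dose (SAP 3.1.3) and may be lower, which leaves still less room. The floor pulls a ratio of geometric means towards 1 for patients with a low baseline.

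**5. Illustration only, if the Protocol 9.4.5 tests were run.** Assumed inputs: 0.5 log10 effect, follow-up SD 0.8 log10, floor 155, 40 vs 20, one-sided 0.05, four baseline shapes from 350 to 10,000,000, stratum cut 10,000, and dependence of change on baseline from none to a slope of −0.5.
- Power at one visit: t test on raw copies 17–36%; t test on log10 change 54–73%; log10 model adjusted for baseline and stratum 70–73%.
- With no true effect, a log10 t test at one named visit gave 4–7% false positives. Adjustment is thus a gain in precision, not the repair of an invalid test.
- With no true effect, counting any success over all 12 visits on log10 gave 13–32% at between-visit correlations of 0.4–0.8. A serially decaying correlation structure with somewhat different inputs gave 14–37%.

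**The case against.** The best defence is that the descriptive reading is dominant. The formal objectives, Protocol 9.1 and the SAP all point that way; the contrary statements sit in narrative text and in a paragraph of the safety section. A proof-of-concept trial with a safety primary endpoint does not need an efficacy test, and every visit and both scales will be shown. This largely stands as a guide to intent. It does not remove the sentence in Protocol 9.4.5, which names BK viral load and sets a threshold. Full display also does not say which result carries the conclusion.

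Several stronger readings are tempting, and the documents do not support them:
- *The SAP softened a test into an assessment.* A reader might infer this from SAP 2.1.2, but the wording matches the protocol's own objectives tables.
- *The planned analysis has an inflated error rate or poor power.* The simulated figures require a test at every visit or a t test on raw copies. No section spells out either, and the SAP contains no efficacy test.
- *Stratum and repeated visits are ignored.* The by-stratum display and the log10 AUC address both, descriptively.
- *Week 12 is the only sensible visit.* It ends the treatment period, but Weeks 8 and 12 must both be on site (Protocol 1.3), and 8 weeks is the timepoint used for resolution of viremia (Protocol 3) and for the interims (Protocol 9.5).

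**Conclusion.** The point holds as a conflict of text and a missing estimate; neither depends on any assumed number. The protocol says both that superiority on BK viral load is tested and that nothing is formally tested. The SAP follows the second without withdrawing the first. In its legible text it names no lead scale, no lead visit or summary, and no between-arm difference, CI or adjustment. Section 9.4.5 also mislabels eGFR.

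The available precision, about 0.55 SD (0.58 SD with 10% missing), is arithmetic from the stated arm sizes; turning it into log10 units needs an assumed SD. The power and error-rate figures are illustrations and not properties of the planned analysis. The safety primary endpoint is unaffected. This should be fixed, but it does not threaten the trial. One reservation is the damaged SAP Table 1, which should be checked in the original.

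**What to change.** 1. **SAP 3.4.1.** Name one lead measure on the log10 scale for pooled PSL against placebo: change at one stated visit, or the time-averaged AUC already planned. Weeks 8 and 12 are both defensible, and the choice is the sponsor's. Estimate it with a model adjusting for baseline log10 viral load and randomisation stratum. Report the difference, also as a ratio of geometric means, with a 95% CI. Give the regimen contrasts from the same model as supportive. Keep the raw-copies, percent-change and by-stratum summaries as descriptive. Note the floor at 155 and that baseline may lie below 350, and show the proportion below the limit beside the estimate.
2. **Timing.** Make the choice before those making it see unblinded comparative data. That includes the Sponsor-run interims in Protocol 9.5, which blind the study team only to individual patient data. If they have already taken place, say so.
3. **Status.** State in the SAP that this estimate replaces the Protocol 9.4.5 test sentence for BK viral load, that any p-value is nominal, and that eGFR is exploratory. Correct the protocol at its next amendment.
4. **Protocol 9.2.** Reconcile the two sample-size statements. If precision is quoted, give about 0.55 residual SD for 40 vs 20 with complete data and about 0.58 with 10% missing.

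The cost is SAP wording and one added model, with no new data, visits or patients. The protocol wording can wait for the next amendment, which goes through IRB/IEC approval (Protocol 10.1.1).
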